8.2.3. Electrocardiograms

- 12-lead ECGs will be obtained as outlined in the SoA (see Section 1.3) using an ECG machine that automatically calculates the heart rate and measures PR, QRS, QT, and corrected QT interval (QTc).
- Electrocardiograms will initially be interpreted by a qualified physician (the investigator or qualified designee) at the site as soon after the time of ECG collection as possible, and ideally while the participant is still present, for immediate participant management, should any clinically relevant findings be identified. Any clinically significant findings from ECGs that result in a diagnosis and that occur after the participant receives the first dose of the study intervention should be reported to Lilly or its designee as an AE via the eCRF.
- All digital ECGs will be obtained using centrally provided ECG machines and will be electronically transmitted to a designated central ECG vendor, except for the screening ECG, which will be performed locally. The central ECG vendor will perform a basic quality control check (for example, demographics and study details) and then store the ECGs in a database. At a future time, the stored ECG data may be overread by a cardiologist at the central ECG vendor for further evaluation of machine-read measurements or to meet regulatory requirements. The machine-read ECG intervals and heart rate may be used for data analysis and report-writing purposes, unless a cardiologist overreading of the ECGs is conducted prior to completion of the final study report (in which case, the overread data would be used).

8.2.4. Clinical Safety Laboratory Assessments

- See Section 10.2, Appendix 2 for the list of clinical laboratory tests to be performed and the SoA for the timing and frequency.
- The investigator must review the laboratory results, document this review, and report any clinically relevant changes occurring during the study as an AE. The laboratory results must be retained with source documents unless a Source Document Agreement or comparable document cites an electronic location that accommodates the expected retention duration. Clinically significant abnormal laboratory findings are those which are not associated with the underlying disease, unless judged by the investigator to be more severe than expected for the participant's condition.

- All laboratory tests with values considered clinically significantly abnormal during participation in the study should be repeated until the values return to normal or baseline or are no longer considered clinically significant by the investigator, or CRP or CRS.
 - If such values do not return to normal/baseline within a period of time judged reasonable by the investigator, the etiology should be identified and the sponsor notified.
 - All protocol-required laboratory assessments, as defined in Section 10.2 Appendix 2, must be conducted in accordance with the SoA and standard collection requirements.
- If laboratory values from non-protocol specified laboratory assessments performed at an investigator-designated local laboratory require a change in participant management or are considered clinically significant by the investigator (e.g., SAE or AE or dose modification), then report the information as an AE.

8.2.5. Hepatic Monitoring

Participants who have abnormal liver tests during the study

Close hepatic monitoring

Laboratory tests (Section 10.5, Appendix 5), including ALT, AST, ALP, total bilirubin, direct bilirubin, γ -glutamyltranspeptidase (GGT), and creatine kinase (CK), should be repeated within 48 to 72 hours to confirm the abnormality and to determine if it is increasing or decreasing, if 1 or more of these conditions occur:

If a participant with baseline results of ...	develops the following elevations:
ALT or AST <1.5x ULN	ALT or AST \geq 3x ULN
ALP <1.5x ULN	ALP \geq 2x ULN
Total bilirubin <1.5x ULN	Total bilirubin \geq 2x ULN (except for participants with Gilbert's syndrome)
ALT or AST \geq 1.5x ULN	ALT or AST \geq 2x baseline
ALP \geq 1.5x ULN	ALP \geq 2x baseline
Total bilirubin \geq 1.5x ULN	Total bilirubin \geq 2x baseline (except for participants with Gilbert's syndrome)

If the abnormality persists or worsens, clinical and laboratory monitoring, and evaluation for possible causes of abnormal liver tests should be initiated by the investigator in consultation with the Lilly-designated CRP or CRS. At a minimum, this evaluation should include physical examination and a thorough medical history, including symptoms, recent illnesses (for example, heart failure, systemic infection, hypotension, or seizures), recent travel, history of concomitant medications (including over-the-counter), herbal and dietary supplements, history of alcohol drinking and other substance abuse.

Initially, monitoring of symptoms and hepatic biochemical tests should be done at a frequency of 1 to 3 times weekly, based on the participant's clinical condition and hepatic biochemical tests. Subsequently, the frequency of monitoring may be lowered to once every 1 to 2 weeks, if the

participant's clinical condition and lab results stabilize. Monitoring of ALT, AST, ALP, and total bilirubin should continue until levels normalize or return to approximate baseline levels.

Comprehensive hepatic evaluation

A comprehensive evaluation (Section 10.5, Appendix 5) should be performed to search for possible causes of liver injury if 1 or more of these conditions occur:

If a participant with baseline results of...	develops the following elevations:
ALT or AST <1.5x ULN	ALT or AST \geq 3x ULN with hepatic signs/symptoms*, or ALT or AST \geq 5x ULN
ALP <1.5x ULN	ALP \geq 3x ULN
Total bilirubin <1.5x ULN	Total bilirubin \geq 2x ULN (except for participants with Gilbert's syndrome)
ALT or AST \geq 1.5x ULN	ALT or AST \geq 2x baseline with hepatic signs/symptoms*, or ALT or AST \geq 3x baseline
ALP \geq 1.5x ULN	ALP \geq 2x baseline
Total bilirubin \geq 1.5x ULN	Total bilirubin \geq 1.5x baseline (except for participants with Gilbert's syndrome)

* Hepatic signs/symptoms are severe fatigue, nausea, vomiting, right upper quadrant abdominal pain, fever, rash, and/or eosinophilia >5%.

At a minimum, this evaluation should include physical examination and a thorough medical history, as outlined above, as well as tests for PT-INR; tests for viral hepatitis A, B, C, or E; tests for autoimmune hepatitis; and an abdominal imaging study (for example, ultrasound or CT scan).

Based on the participant's history and initial results, further testing should be considered in consultation with the Lilly's CRP or CRS, including tests for hepatitis D virus (HDV), cytomegalovirus (CMV), Epstein-Barr virus (EBV), acetaminophen levels, acetaminophen protein adducts, urine toxicology screen, Wilson's disease, blood alcohol levels, urinary ethyl glucuronide, and blood phosphatidylethanol. Based on the circumstances and the investigator's assessment of the participant's clinical condition, the investigator should consider referring the participant for a hepatologist or gastroenterologist consultation, magnetic resonance cholangiopancreatography (MRCP), endoscopic retrograde cholangiopancreatography (ERCP), cardiac echocardiogram, or a liver biopsy.

Additional hepatic data collection (hepatic safety eCRF) in study participants who have abnormal liver tests during the study

Additional hepatic safety data collection in hepatic safety eCRF should be performed in study participants who meet 1 or more of the following 5 conditions:

1. Elevation of serum ALT to \geq 5x ULN on 2 or more consecutive blood tests (if baseline ALT <1.5x ULN)
 - In participants with baseline ALT \geq 1.5x ULN, the threshold is ALT \geq 3x baseline on 2 or more consecutive tests
2. Elevated total bilirubin to \geq 2x ULN (if baseline total bilirubin <1.5x ULN) (except for cases of known Gilbert's syndrome)

- In participants with baseline total bilirubin $\geq 1.5x$ ULN, the threshold should be Total bilirubin $\geq 2x$ baseline
- 3. Elevation of serum ALP to $\geq 2x$ ULN on 2 or more consecutive blood tests (if baseline ALP $< 1.5x$ ULN)
 - In participants with baseline ALP $\geq 1.5x$ ULN, the threshold is ALP $\geq 2x$ baseline on 2 or more consecutive blood tests
- 4. Hepatic event considered to be an SAE
- 5. Discontinuation of study intervention due to a hepatic event

Note: the interval between the 2 consecutive blood tests should be at least 2 days.

8.3. Adverse Events, Serious Adverse Events, and Product Complaints

The definitions of the following events can be found in Section 10.3, Appendix 3:

- AEs
- SAEs
- Product complaints (PCs)

These events will be reported by the participant (or, when appropriate, by a caregiver, surrogate, or the participant's legally authorized representative).

The investigator and any qualified designees are responsible for detecting, documenting, and recording events that meet these definitions and remain responsible for following up events that are serious, considered related to the study intervention or study procedures, or that caused the participant to discontinue the study intervention or study (see Section 7).

Care will be taken not to introduce bias when detecting events. Open-ended and non-leading verbal questioning of the participant is the preferred method to inquire about event occurrences.

After the initial report, the investigator is required to proactively follow each participant at subsequent visits/contacts. All SAEs and AEs of special interest (as defined in Section 8.3.3) will be followed until resolution, stabilization, the event is otherwise explained, or the participant is lost to follow-up (as defined in Section 7.3). For product complaints, the investigator is responsible for ensuring that follow-up includes any supplemental investigations as indicated to elucidate the nature and/or causality. Further information on follow-up procedures is provided in Appendix 10.3.

8.3.1. Timing and Mechanism for Collecting Events

This table describes the timing, deadlines, and mechanism for collecting events.

Event	Collection Start	Collection Stop	Timing for Reporting to Sponsor or Designee	Mechanism for Reporting	Back-up Method of Reporting
Adverse Event					
AE	signing of the informed consent form (ICF)	the follow-up visit	As soon as possible upon site awareness	AE eCRF	N/A
Serious Adverse Event					
SAE and SAE updates – prior to start of study intervention and deemed reasonably possibly related with study procedures	signing of the ICF	start of intervention	Within 24 hours of awareness	SAE eCRF	SAE paper form
SAE and SAE updates – after start of study intervention	start of intervention	participation in study has ended	Within 24 hours of awareness	SAE eCRF	SAE paper form
SAE – after participant's study participation has ended and the investigator becomes aware	After participant's study participation has ended	N/A	Promptly	SAE paper form	N/A
Pregnancy					
Pregnancy in female participants and female partners of male participants	After the start of study intervention	4 weeks after the last dose of study intervention	Within 24 hours of learning of the pregnancy	SAE eCRF ^a	SAE paper form

Event	Collection Start	Collection Stop	Timing for Reporting to Sponsor or Designee	Mechanism for Reporting	Back-up Method of Reporting
Product Complaints					
Product Complaints (PC) associated with an SAE or might have led to an SAE	Start of study intervention	End of study intervention	Within 24 hours of awareness	Product Complaint form ^b	N/A
PC not associated with an SAE	Start of study intervention	End of study intervention	Within 1 business day of awareness	Product Complaint form ^b	N/A
Updated PC information	—	—	As soon as possible upon site awareness	Originally completed Product Complaint form with all changes signed and dated by the investigator	N/A
PC (if investigator becomes aware) ^c	Participation in study has ended	N/A	Promptly	Product Complaint form	

^a Pregnancy itself is not considered to be an AE or SAE. However, to fulfill regulatory requirements any pregnancy should be reported following the SAE process to collect data on the outcome for both mother and fetus.

^b AEs and SAEs that are associated with a product complaint will also follow the processes outlined in Section 8.3.

^c The PC which the investigator becomes aware of after the study has ended.

8.3.2. Pregnancy

Pregnancy (maternal or paternal exposure to study intervention) does not meet the definition of an adverse event. However, to fulfill regulatory requirements, any pregnancy should be reported following the SAE process described in Appendix 10.3 to collect data on the outcome for both mother and fetus.

8.3.3. Adverse Events of Special Interest

Adverse events of special interest (AESIs) for this program include:

- a. Hypoglycemia
- b. Severe, persistent hyperglycemia

- c. Pancreatitis
- d. C-cell hyperplasia and C-cell neoplasms
- e. Cardiovascular events
- f. Hypersensitivity reactions

If a, b, c, d, e, or f are reported, sites will be prompted to collect additional details/data on the specific eCRFs.

Hypoglycemia

Participants will collect information on episodes of hypoglycemia starting from Visit 3 (Week 0) until the last study visit (ET visit or Visit 801). Participants will be trained about signs and symptoms of hypoglycemia, how to treat hypoglycemia, and how to collect appropriate information for each episode of hypoglycemia in the study according to the SoA (Section 1.3). Site personnel will enter this information into the hypoglycemia eCRF at each visit.

Investigators should use the following definitions and criteria when diagnosing and categorizing an episode considered to be related to hypoglycemia (the BG values in this section refer to values determined by a laboratory or International Federation of Clinical Chemistry and Laboratory Medicine plasma-equivalent glucose meters and strips) in accordance with the 2020 ADA position statement on glycemic targets:

Level 1 hypoglycemia

Glucose <70 mg/dL (3.9 mmol/L) and \geq 54 mg/dL (3.0 mmol/L): Level 1 hypoglycemia can alert a person to take action such as treatment with fast-acting carbohydrates. Providers should continue to counsel participants to treat hypoglycemia at this glucose alert value.

Level 2 hypoglycemia

Glucose <54 mg/dL (3.0 mmol/L): Level 2 hypoglycemia is also referred to as documented or blood glucose confirmed hypoglycemia with glucose <54 mg/dL (3.0 mmol/L). This glucose threshold is clinically relevant regardless of the presence or absence of symptoms of hypoglycemia.

Level 3 hypoglycemia

Severe hypoglycemia (in adults): A severe event characterized by altered mental and/or physical status requiring assistance for treatment of hypoglycemia. For example, participants had altered mental status, and could not assist in their own care, or were semiconscious or unconscious, or experienced coma with or without seizures, and the assistance of another person was needed to actively administer carbohydrate, glucagon, or other resuscitative actions. Glucose measurements may not be available during such an event, but neurological recovery attributable to the restoration of glucose concentration to normal is considered sufficient evidence that the event was induced by a low glucose concentration.

- The determination of a hypoglycemic event as an episode of severe hypoglycemia, as defined above, is made by the investigator based on the medical need of the participant to have required assistance and is not predicated on the report of a participant simply having received assistance.

- If a hypoglycemic event meets the criteria of severe hypoglycemia, the investigator must record the event as serious on the AE eCRF and report it to Lilly as an SAE.

Nocturnal hypoglycemia

Nocturnal hypoglycemia is a hypoglycemia event (including severe hypoglycemia) that **occurs at night** and presumably during sleep.

To avoid duplicate reporting, all consecutive BG values occurring within a 1-hour period may be considered to be a single hypoglycemic event (Weinberg et al. 2010; Danne et al. 2013; ADA 2020).

In each case of suspected or confirmed hypoglycemia, it is important that the event be properly categorized, the effect of the intervention be assessed, and the frequency of hypoglycemia be evaluated. The role of dietary changes and physical exercise (or any other contributing factor) in the development of an event should be established. The participant should receive additional education, if deemed appropriate. It is important that each case of suspected or confirmed hypoglycemia be properly categorized with respect to severity.

Severe Persistent Hyperglycemia

Severe, persistent hyperglycemia will be collected as an AE during the study to assess the risk of extreme imbalance in glycemic control, as defined in Section 6.5.1. Details of antihyperglycemic medication initiated as rescue therapy for severe, persistent hyperglycemia per these criteria will be collected on the antihyperglycemic concomitant therapy eCRF.

Pancreatitis

Diagnosis of acute pancreatitis

Acute pancreatitis is defined as an AE of interest in all studies with dulaglutide, including this study.

Acute pancreatitis is an acute inflammatory process of the pancreas that may also involve peripancreatic tissues and/or remote organ systems (Banks and Freeman 2006; Koizumi 2006).

The diagnosis of acute pancreatitis requires 2 of the following 3 features:

- abdominal pain, characteristic of acute pancreatitis (generally located in the epigastrium and radiates to the back in approximately half the cases [Banks and Freeman 2006; Koizumi et al. 2006]; the pain is often associated with nausea and vomiting);
- serum amylase (total, pancreatic, or both) and/or lipase $\geq 3 \times$ ULN;
- characteristic findings of acute pancreatitis on computed tomography (CT), scan or magnetic resonance imaging (MRI)

If acute pancreatitis is suspected, the investigator should

- obtain appropriate laboratory tests, including pancreatic amylase (p-amylase) and lipase
- perform imaging studies, such as abdominal CT scan with or without contrast, or abdominal MRI
- evaluate for possible causes of acute pancreatitis, including alcohol use, gallstone/gall bladder disease, hypertriglyceridemia, and concomitant medications.

Each case of pancreatitis must be reported. If typical signs and/or symptoms of pancreatitis are present and confirmed by laboratory values (lipase or amylase [total and/or pancreatic]) and imaging studies, the event must be reported as an SAE. For a potential case that does not meet all of these criteria, it is up to the investigator to determine the seriousness of the case (AE or SAE) and the relatedness of the event to study intervention.

Discontinuation for acute pancreatitis

If acute pancreatitis is diagnosed, the participant must discontinue use of the study intervention.

Case adjudication and data entry

An independent clinical endpoint committee (CEC) will adjudicate all suspected cases of acute pancreatitis. Only cases of pancreatic hyperenzymemia that undergo additional diagnostic follow-up and/or are accompanied by symptoms suggestive of pancreatitis will be submitted for adjudication. In addition, AEs of severe or serious abdominal pain of unknown etiology will also be submitted to the adjudication committee to assess for possible pancreatitis or other pancreatic disease. Relevant data from participants with acute or chronic pancreatitis and those with severe or serious abdominal pain will be entered into a specifically designed eCRF page by study site or Lilly staff. The adjudication committee representative will enter the results of adjudication in a corresponding eCRF page.

Asymptomatic elevation of serum amylase and/or lipase

Each participant will have measurements of pancreatic amylase and lipase (assessed at the central laboratory) as shown on the SoA (Section 1.3), to assess the effects of the investigational doses of dulaglutide on pancreatic enzyme levels.

Serial measures of pancreatic enzymes have limited clinical value for predicting episodes of acute pancreatitis in asymptomatic participants (Nauck et al. 2016; Steinberg et al. 2017a, 2017b). Therefore, further diagnostic follow-up of cases of asymptomatic elevation of pancreatic enzymes (lipase and/or p-amylase $\geq 3X$ ULN) is not mandated but may be performed based on the investigator's clinical judgment and assessment of the participant's overall clinical condition.

C-Cell Hyperplasia and C-Cell Neoplasms

Individuals with personal or family history of certain thyroid or nonthyroid endocrine abnormalities or certain preexisting laboratory and genetic characteristics will be excluded from the study (see Section 5.2). Participants with a personal or family history of MTC or personal history of MEN 2 syndrome, or who have serum calcitonin ≥ 20 pg/mL at study entry as determined by the central laboratory will be excluded. The assessment of thyroid safety during the study will include reporting of thyroid TEAEs and measurements of calcitonin according to the SoA (Section 1.3). The purpose of calcitonin measurements is to assess the potential of dulaglutide to affect thyroid C-cell function, which may indicate development of C-cell hyperplasia and neoplasms.

Participants who develop serum calcitonin increases $\geq 50\%$ of the screening value AND an absolute value ≥ 20 pg/mL and < 35 pg/mL at Visit 7 (Week 26) will be asked to repeat the measurement within 1 month. If this repeat value is increasing ($\geq 10\%$ increase), the participant will be encouraged to undergo additional endocrine assessment and longer-term follow-up by an endocrinologist to exclude a serious adverse effect on the gland.

Participants with an increase in serum calcitonin $\geq 50\%$ of screening value AND an absolute value ≥ 35 pg/mL at Visit 7 (Week 26) will be recommended to immediately undergo additional endocrine assessments and longer-term follow-up by an endocrinologist.

For participants who require additional endocrine assessment because of increased calcitonin concentration per criteria provided in this section, data from the follow-up assessment will be collected in the specific section of the eCRF.

Cardiovascular Events

Vital signs (PR, systolic blood pressure [SBP], diastolic blood pressure [DBP]) will be monitored throughout the study, and 12-lead ECGs will be monitored per the SoA (Section 1.3). Any clinically relevant finding from vital signs and ECGs obtained before the first dosing of study intervention that results in a diagnosis should be recorded in the eCRF as a preexisting condition and medical history. Any clinically relevant finding from vital signs and ECGs that occurs after the first dosing of study intervention and results in a diagnosis should be recorded as an AE in eCRF. Cardiovascular events will be analyzed using preferred terms and abnormal ECG result.

Hypersensitivity Reactions

All hypersensitivity reactions will be reported by the investigator as either AEs or, if any serious criterion is met, as SAEs. Additional data, such as type of reaction and treatment received, will be collected on the hypersensitivity reaction eCRF for any AEs or SAEs deemed related to study intervention by the investigator. In the event of severe hypersensitivity reactions (i.e., generalized urticaria or anaphylaxis), serum and plasma samples should also be collected as close as possible to the occurrence of the event. Samples for follow-up assessment may also be collected within 4 weeks of the recovery from the event. Study intervention should be temporarily interrupted in any individual suspected of having a severe or serious allergic reaction to study intervention (Section 7.1.1). Study intervention may be restarted when/if it is safe to do so, in the opinion of the investigator. It is recommended that participants who experience a systemic hypersensitivity reaction be treated per the local standard of care.

If study intervention is permanently discontinued, the participant will receive another glucose-lowering treatment, judged by the investigator to be appropriate based on the participant's clinical status, and will continue in the study to collect all planned efficacy and safety measurements.

Injection site reactions will be collected on an eCRF separate from the hypersensitivity reaction eCRF.

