At Week 52 or the early termination (ET) visit, all used and unused study intervention will be returned.

Discontinuation or dose changes of concomitant OAMs are not permitted, except in certain situations (Section 6.5). Participants will be permitted to use concomitant medications that they require during the study, except certain medications that may interfere with the assessment of efficacy and safety characteristics of the study intervention (Section 6.5).

Safety Follow-Up Period

Procedures during the safety follow-up period will be performed as shown in the SoA (Section 1.3).

All participants who complete the treatment period (both I and II) are required to complete Visit 801, a safety follow-up visit approximately 4 weeks after the last visit of the treatment period. During the safety follow-up period, participants will not receive study intervention.

The safety follow-up period will also be applied to participants who discontinue from the study. In this case, the Safety Follow-Up visit (Visit 801) will occur approximately 4 weeks after the ET visit.

Participants are required to return any remaining study diaries to the study site at the end of this period.

Early Termination Visit

Every attempt will be made to keep participants in the study irrespective of their adherence to treatment with study intervention.

At any time after Visit 3 (randomization), a participant who is to discontinue from the study before Visit 9 will have an ET visit conducted. At this visit, procedures will occur as shown in the SoA (Section 1.3). Participants should be instructed to return any remaining used or unused study intervention supplies and diaries to the study site at this visit. Participants will be asked to perform the Safety Follow-Up visit (Visit 801) approximately 4 weeks after the ET visit, so that the Safety Follow-Up visit (Visit 801) will be their final visit. If the participant is not able to perform the Safety Follow-Up visit (Visit 801), the ET visit will be the final study visit. A participant summary electronic case report form (eCRF) will be completed.

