7.1. Discontinuation of Study Intervention

In rare instances, it may be necessary for a participant to permanently discontinue (definitive discontinuation) study intervention. If study intervention is definitively discontinued, the participant will remain in the study to be evaluated for all planned efficacy and safety measurements. See the SoA (Section 1.3) for data to be collected at the time of discontinuation of study intervention and follow-up and for any further evaluations that need to be completed.

Possible reasons leading to permanent discontinuation of study intervention include:

Participant Decision

The participant requests to discontinue study intervention.

Discontinuation due to a hepatic event or liver test abnormality.

Participants who are discontinued from study intervention due to a hepatic event or liver test abnormality should have additional hepatic safety data collected via the eCRF (Section 10.5, Appendix 5). Discontinuation of the study intervention for abnormal liver tests **should be** considered by the investigator when a participant meets 1 of the following conditions after consultation with the Lilly's CRP or CRS:

- ALT or aspartate aminotransferase (AST) >8X upper limit of normal (ULN)
- ALT or AST >5X ULN for more than 2 weeks
- ALT or AST >3X ULN and total bilirubin level (TBL) >2X ULN or international normalized ratio (INR) >1.5
- ALT or AST >3X ULN with the appearance of fatigue, nausea, vomiting, right upper-quadrant pain or tenderness, fever, rash, and/or eosinophilia (>5%)
- Alkaline phosphatase (ALP) >3X ULN
- ALP >2.5X ULN and TBL >2X ULN
- ALP >2.5X ULN with the appearance of fatigue, nausea, vomiting, right quadrant pain or tenderness, fever, rash, and/or eosinophilia (>5%)

Additional circumstances in which participants will be discontinued from the study intervention include:

A participant will be discontinued from study intervention due to any of the following:

- If a participant is inadvertently enrolled and it is determined that continued study intervention would not be medically appropriate (See Section 7.2.1)
- If a participant misses 3 continuous injections
- Acute or chronic pancreatitis

- If a participant is diagnosed with an active or untreated malignancy (other than basal or squamous cell skin cancer, in situ carcinomas of the cervix, or in situ prostate cancer) after randomization
- If a participant is diagnosed with C-cell hyperplasia or medullary thyroid carcinoma (MTC) after randomization

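### Both calcitonin follow-up rules apply only at Week 26, so the same rise first seen at Visit 9, early termination or Visit 801 has no threshold-based referral or matching eCRF capture

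*Protocol*

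**What the plan says.** Protocol 8.3.3 (C-Cell Hyperplasia and C-Cell Neoplasms) has two action rules. Both require a rise of at least 50% over the screening value.

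- **20 to <35 pg/mL.** The participant "at Visit 7 (Week 26) will be asked to repeat the measurement within 1 month". If the repeat is at least 10% higher, endocrine assessment and longer-term follow-up are encouraged. The stated purpose is "to exclude a serious adverse effect on the gland".
- **35 pg/mL or more.** The participant "at Visit 7 (Week 26) will be recommended to immediately undergo additional endocrine assessments".

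For participants who need assessment under these criteria, "data from the follow-up assessment will be collected in the specific section of the eCRF". That capture carries the same visit limit, because it depends on the criteria.

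The Schedule of Activities (1.3) places calcitonin at Visits 1, 3, 7 (Week 26), 9 (Week 52), ET and 801 (Week 56). Under 4.1, a participant who leaves the study has an ET visit, and "the Safety Follow-Up visit (Visit 801) will occur approximately 4 weeks after the ET visit". If Visit 801 cannot be done, "the ET visit will be the final study visit". A participant who stops only the drug is treated differently under 7.1: "the participant will remain in the study to be evaluated for all planned efficacy and safety measurements".

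**The concern.** The same laboratory result gets a different protocol response depending on when it is first seen. C-cell disease is an adverse event of special interest, and the reason given for referral is as valid at Week 52 as at Week 26. Section 4.2 says the 52-week duration was chosen to assess long-term efficacy and safety, yet a rise that first appears in the second half of treatment falls outside both rules.

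The protocol does not take this approach for the liver. Clinical chemistry is scheduled at the same visits as calcitonin, and the numeric hepatic triggers in 8.2.5 apply throughout the study. No reason is given for the difference.

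At stake are the consistency of referral and the completeness of follow-up data. The SAP's calcitonin shift table (4.6.3.1) uses the maximum post-baseline value, so a late rise can appear in the report without any criteria-based follow-up record to explain it. The SAP's C-cell summary (4.6.3.5.3) is built from thyroid cancer terms and C-cell hyperplasia, so an isolated calcitonin rise does not enter it.

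**Working it through.** **1. Which samples the rules cover.** Inputs: the calcitonin row in Protocol 1.3, the visit limit in 8.3.3, and the ET and Visit 801 provisions in 4.1.

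| Participant | Post-baseline samples | Under the rules | No rule, later sample scheduled | Neither |
|---|---|---|---|---|
| Completer | Visits 7, 9, 801 | 1 (Visit 7) | 1 (Visit 9) | 1 (Visit 801) |
| Leaves the study after Visit 7 | Visit 7, ET, 801 | 1 (Visit 7) | 1 (ET) | 1 (Visit 801) |
| Leaves before Week 26 | ET, 801 | 0 | 1 (ET) | 1 (Visit 801) |
| Leaves before Week 26, Visit 801 not attended | ET | 0 | 0 | 1 (ET) |

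Section 9.2 plans 585 randomized and 528 evaluable: 585 − 528 = 57, and 57/585 = 9.7%. If all 57 left the study before Week 26, that would be the planned ceiling on participants with no covered sample. It says nothing about how many would have a rise.

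**2. Timing of Visit 801 as a repeat.** Visit 9 is day 52 × 7 = 364 and Visit 801 is day 56 × 7 = 392, each ±7 days.

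- Nominal gap: 392 − 364 = 28 days.
- Shortest: (392 − 7) − (364 + 7) = 14 days.
- Longest: (392 + 7) − (364 − 7) = 42 days.
- Exceptional circumstances (10.8: 4 weeks after Visit 9, −7 to +28 days): 21 to 56 days.

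So Visit 801 usually falls within about a month, but not always. It is also off drug: "During the safety follow-up period, participants will not receive study intervention".

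**3. How the thresholds behave.**

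- Exclusion criterion 21 requires calcitonin below 20 pg/mL at entry. Since 35/20 = 1.75, any later value of 35 or more is a rise of more than 75% and always meets the 50% condition.
- Take 22 pg/mL followed by 25. The step is 25/22 = 1.136, a rise of 13.6%, above 10%. For 22 to qualify in the first place, the screening value must be at most 22/1.5, about 14.6 pg/mL. With that condition, the pair leads to encouraged endocrine assessment if 22 is the Visit 7 value, and meets no stated criterion if the two values come from Visits 9 and 801.
- Reverse the pair: 25 on drug at Visit 9, then 22 off drug at Visit 801. The ratio is 22/25 = 0.88, so the 10% step does not trigger. Yet 22 is still at least 20, and with a screening value of 14.6 it is still 22/14.6 = 1.51 times screening. The 10% step alone could falsely reassure after dosing stops.

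**4. What applies at the later visits.**

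| Provision | Applies at Visit 9, ET, 801? | What sets it off |
|---|---|---|
| 8.3.3 thresholds, referral, criteria-based eCRF | No | Numeric criteria at Visit 7 |
| 8.2.4 review, AE reporting, repeats, etiology and sponsor notification if the value stays abnormal | Yes | Investigator judges the value clinically significant |
| 8.3.1 and 10.3.4 AE collection to the follow-up visit, with an obligation to arrange medically indicated evaluations, which may include specialist consultation | Yes | Rise reported as an AE |
| 8.3.3 AESI eCRF prompt; 8.3 follow-up of the event | Yes | C-cell event reported |
| SAP 4.6.3.1 shift table and abnormal-result listings | Yes | Any value |

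None of the provisions that apply at the later visits carries a calcitonin threshold or names an endocrinologist.

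**The case against.** The strongest reply is that the general safety provisions already do the work. A clinically significant rise is an AE up to the follow-up visit, and 10.3.4 obliges the investigator to arrange what is medically indicated. That is stronger wording than the Visit 7 rules, which only ask, encourage or recommend. Investigators are diabetology specialists (10.1.10), extra tests are allowed at any time during the study (10.2), and late values reach the SAP outputs because the 52-week safety set includes the follow-up period. This stands, and it limits the point. It does not close the gap, because the AE route starts only once the investigator judges the rise clinically significant.

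A second reply is that the limit may be deliberate: Visit 7 is the only scheduled post-baseline calcitonin sample with further planned dosing after it. That is plausible, but the protocol does not say so. Neither rule acts on dosing either; under 7.1 the drug is stopped on a diagnosis, not on a calcitonin level.

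A reader might infer that a late rise goes unhandled, that participants would stay exposed after one, or that everyone who stops the drug early escapes the rules. The documents support none of these. The general provisions apply, dosing has ended by Visit 9, ET and Visit 801, and participants who stop only the drug remain in the study and are due for Visit 7.

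**Conclusion.** The point holds as a narrow one. At Visit 9, ET and Visit 801 the protocol lacks three things that it provides at Visit 7: the numeric trigger, the named endocrinologist referral and the eCRF capture tied to both. The rules cover 1 of 3 post-baseline samples in a completer and 0 of 2 in a participant who leaves the study before Week 26. The exposed cases are above all a rise first seen at Visit 801, or at ET when Visit 801 is not attended, because no further sample is then scheduled.

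The number of participants affected cannot be estimated, since the documents give no rate of qualifying rises. The consequence is uneven referral and follow-up data for a safety topic of special interest. The primary analysis, sample size and type I error are unaffected. This is an optional, cheap improvement.

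**What to change.** In both rules of Protocol 8.3.3, replace the Visit 7 restriction with *at any post-baseline measurement (Visit 7, Visit 9, ET or Visit 801)*, and keep the same eCRF capture while the participant is in the study. Then specify:

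- **35 pg/mL or more at any of these visits:** recommend referral immediately, without waiting for Visit 801.
- **20 to <35 pg/mL with a rise of at least 50%, at Visit 9 or ET:** use the scheduled Visit 801 sample as the repeat, accepting its window. Because it is taken off drug, recommend endocrine referral if it is at least 10% higher *or* still meets the 50% and 20 pg/mL criteria.
- **The same range first seen at Visit 801, or at ET when Visit 801 is not attended:** recommend referral through usual care.

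The Visit 7 steps themselves stay as they are.

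The cost is protocol wording in two rules; every sample used is already scheduled. The downside is a few extra referrals and a small provision for recording their results, since Visit 801 is the last visit and the electronic tool goes off-line once a site has completed the study (10.3.5). Serious outcomes learned of later already have the paper SAE form (8.3.1).
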